13.3 STATISTICAL METHODS

13.3.1 Primary Outcome - Reduction in SOWS-Gossop criterion. The primary outcome will be reduction in subjective withdrawal as measured by the SOWS - Gossop (scores range from zero to 30). The groups will be compared on the 14 repeated SOWS-Gossop responses obtained during the seven-day detoxification period, using linear mixed-effects regression models; the SOWS-Gossop total will be regressed on a three-level factor for site, and a two-level factor for medication group, with time and group by time effects. The covariance structure will include a random intercept and correlated residuals, with a random slope included if necessary for fit. Contrasts between the PGB group and the PGB-PLA group will be estimated from the model. Exploratory analyses of heterogeneity of dose effects across sites will be performed including a site by dose interaction term in the main model.

These models will provide valid estimates and tests if any missing data is statistically ignorable (Laird, 1998). Dropout may be associated with reports of subjective withdrawal, and will be ignorable if available subjective scores prior to dropout are predictive of dropout. To assess possible effects of non-ignorability on inference, we will perform sensitivity analyses using pattern- mixture models and selection models. For pattern mixture models, subjects are grouped on the basis of their pattern of missing data. Usually, rarely occurring patterns are grouped, so as to keep the number of pattern-groups at a manageable level. This grouping defines a nominal variable, which is then used as a predictor in the analyses, although a covariate representing missingness on a continuous scale can also be used. The regression coefficients associated with this variable, and its interactions with the other predictors, quantify how response-predictor relationships differ across the different patterns of missingness. Overall predictor effects may be found by averaging over the patterns (Little, 1993). For longitudinal data, subjects are usually stratified according to the visit after which they dropped out. Hedeker and Gibbons (1997), and Hedeker and Rose (2000), apply these methods to mixed effects models in longitudinal data. Selection models (Little, 1995; Kenward, 1998; Verbeke and Molenberghs, 2000) take a different approach, by explicitly modeling the probability of drop out, and incorporating the predicted probabilities

into the main longitudinal analysis. Heuristically, this can be thought of as a two-stage process, but usually the two steps are performed as part of a single model. Any approach to non-ignorability requires us to make assumptions on the variables associated with missing data, and on the form of the relationship between the variables and dropout. Comparisons between the predictions of the primary analyses, and each set of pattern mixture and selection models, provides some evidence for assessing the sensitivity of results to missing data.

13.3.2 Secondary Outcomes. Completion of and receipt of antagonist treatment: Our completion threshold criterion is based on the study of Fishman et al (2019), where completion of detoxification was defined as "proportion of participants completing the study, defined as having received at least 1 dose of study medication on day 7 and completing the 3.5- hour post dose SOWS-Gossop assessment on day 7. Receipt of antagonist treatment will be defined as completion of the process to receive antagonist treatment and receipt of the first dose.

We will define a three-category ordinal response: (1) failure to complete detoxification, (2) completion with failure to start antagonist treatment, (3) completion and receipt of antagonist treatment. We will compare these groups using ordinal logistic regression models, with a three-level factor for site, and a two-level factor for medication group, as the explanatory variables.

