7.3.2 DOSING SCHEDULES

Table 2: LFX Dosing: all tablets are 0.18 mg

	Time	Day 1	Day 2	Day 3	Day 4	Day 5	Day 6	Day 7
All	0800	0.00	0.54	0.54	0.54	0.54	0.36	0.18
Groups								
	1200	0.54	0.54	0.54	0.54	0.36	0.18	0.18
	1600	0.54	0.54	0.54	0.54	0.36	0.18	0.18
	2000	0.54	0.54	0.54	0.54	0.36	0.18	0.18
	Total	1.62	2.16	2.16	2.16	1.62	0.90	0.72

Table 3: PGB and PGB-PLA Dosing (in mg)

	Time	Day 1	Day 2	Day 3	Day 4	Day 5	Day 6	Day 7
Group 1	0800	0	200	200	200	100	50	25
(PGB)	1200	100	100	100	100	75	25	25
	1600	100	100	100	100	75	25	25
	2000	200	200	200	200	150	100	25
	Total	400	600	600	600	400	200	100
Group 2	0800	0	PLAC	PLAC	PLAC	PLAC	PLAC	PLAC
(PGB-PLA)	1200	PLAC						
	1600	PLAC						
	2000	PLAC						
	Total	0	0	0	0	0	0	0

7.3.3 Dosing Guidelines:

As stated below investigators may choose to stop or reduce the dose of either Study Medication although BP and pulse changes are more likely to be due to lofexidine and sedation due to pregabalin.

- Patients can be started and continued on Study Medication if the pulse is 50 or above. Medication should be held if the pulse is <50.
- Patients can be started on Study Medications on Day 1 if COWS >/=6 and SOWS_>/= 4
- A study physician is required to hold the dose of Study Medication if the systolic BP is < 90 and/or the diastolic is <60. Investigators should hold both lofexidine and pregabalin until the next dosing time when they can be restarted if the vitals return to 90/60 or above.
- Hypotension is a potential side effect of lofexidine; sedation, dizziness, or light-headedness are
 potential side effect of pregabalin. A drop of 20 mm or more systolic and/or 10 mm or more diastolic;
 or significant lightheadedness or dizziness, are grounds for holding or reducing a dose of the
 medication that is the most likely cause. Investigators should use their judgement on which Study
 Medication to hold or reduce and by how much.
- **7.3.3.1** The following procedures will minimize risks associated with transient vs. persistent BP changes:
 - If the BP reading shows a pre-medication sitting and/or standing drop (orthostatic change) of more than 20mm systolic, and/or more than 10 mm diastolic, wait 2-3 minutes and repeat the sitting and standing BP.

- If the repeat readings are within the acceptable range as defined by the protocol, dosing can be continued as planned.

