- If the repeated readings are not within this range as defined by the protocol, hydrate the patient and study medication should be administered at the next scheduled dosing time provided they are in an acceptable range, as defined by the protocol. Retest the BP within an hour. Depending on the results of the BP retest, the physician has the discretion to give full dose, reduced dose, or hold the dose of study medication until the next scheduled dosing time.

Dosing should be given per the protocol scheduled times of 8:00, 12:00, 16:00, and 20:00. However, when dosing cannot be given at the protocol scheduled times, Study Medication can be given up to 1 hour pre or post the scheduled dose time. On day 1, if dosing cannot be given at the 12:00 scheduled time, after 2 hours, wait until the next scheduled 16:00 dose. In case of scheduled dosing changes, medication cannot be scheduled less than a minimum of 3 hours apart.

- **7.3.4** Potential Risks: These include AEs to PGB, LFX, and XR-NTX (for those who transition to it); potential adverse interactions between PGB and LFX; and a small risk from venipuncture. Clinical trials are conducted under widely varying conditions thus adverse reaction rates in clinical trials cannot be directly compared to rates in clinical trials of another similarly-acting drug, and may not reflect the rates observed in clinical practice.
- **7.3.5_PGB associated AE's:** In controlled and uncontrolled trials across various patient populations during premarketing development more than 10,000 patients received PGB; approximately 5000 for 6 months or more; over 3100 for 1 year or more; and over 1400 for at least 2 years.
- **7. 3. 6** Most common AE's leading to discontinuation of PGB. In premarketing trials of all populations combined, 14% of patients treated with PGB and 7% of patients treated with placebo discontinued treatment prematurely due to AEs. AEs most frequently leading to discontinuation were dizziness (4%) and somnolence (3%). In the placebo group, 1% of patients withdrew due to dizziness and <1% withdrew due to somnolence. Other adverse reactions that led to discontinuation more frequently in the PGB group compared to placebo were ataxia, confusion, asthenia, thinking abnormal, blurred vision, incoordination, and peripheral edema (1% each).

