Subjects are admitted to the inpatient unit, randomized to one of the two study medication conditions, and will need to demonstrate withdrawal before starting study medications by having a COWS >/= 6 and a SOWS >/= 4. LFX and PGB dosing will begin at 12:00 on day 1 and a study drug taper will be done from days 5-7. Dose times follow the schedule outlined above and adjustments will be made based on BP changes and/or other AEs. Administration of LFX will be withheld or reduced in cases of dizziness or lightheadedness, clinically significant hypotension and/or the BP changes described above. We will explain to participants the importance for adequate oral hydration during the consenting process and throughout the detox. Similar procedures will be applied to PGB in cases of excessive sedation, dizziness, peripheral edema, or other problematic side effects that appear related that medication.

Dosing schedules are in Tables 2 and 3. Assessments for Day 1 through 7 include:

- 1) ECG is obtained before the 12:00 dose of study medications on Day 1 and before the 08:00 dose of study medications on Day 2-7
- 2) VAS is given before the first dose of study medication at 12:00 on Day 1 and before the 16:00 dose on Day 1. On Day 2-7, the VAS is given before the first dose of study medications at 08:00 and before the 16:00 dose of study medications
- 3) ISI given before the 12:00 dose of study medications on Day 1, and before the 08:00 dose of study medications on Days 2-7
- 4) COWS is given around 12:00 on Day 1 before the first dose of study medication; and around16:00 before the next dose of study medication. If subject is admitted without the requisite withdrawal (COWS >/= 6 and SOWS >/= 4), subsequent COWS and SOWS can be administered before the first dose of study medication until dosing criteria is met.
- 5) SOWS-G is given around 12:00 on Day 1 before the first dose of study medication; and around 16:00 before the next dose of study medication
- 6) POSS is given prior to all doses (08:00, 12:00, 16:00 and 20:00) of study medication
- 7) Sitting and standing blood pressure and pulse are taken prior to each dose of study medication and 1 to 2 hours after dosing, (can use manual blood pressure check if considered necessary)
- 8) Weight taken 1x at screen and Day 15 and recorded on the physical form
- 9) Adverse events/SAEs recorded daily
- 10) Concomitant medication records reviewed and recorded each day
- 11) C-SSRS is given at the end of each study day

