11.0 METHODS FOR ASSIGNING SUBJECTS TO TREATMENT GROUPS

11.1 RANDOMIZATION

[name] will develop a program using computer-generated, randomly permuted blocks within each site

that are stratified according to male/female. Upon completing screening assessments, research staff will request randomization be performed by the site research pharmacy. The patient will be sequentially assigned to the next treatment based on male/female status. At all sites, patient treatment will correspond to a unique randomization number.

Penn IDS will upload the randomization lists into a Treatment Unmasking Program, per IDS SOP-309. Access to this trial within the program will be provided to authorized Penn users. In the event of an emergency, unmasking can occur at any time using the subject's assigned randomization number. The user will not be unmasked to the treatment of other subjects. For other sites, [name] will give the randomization list to PENN IDS who will be responsible for maintaining the randomization blind.

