13.0 STATISTICAL PLAN

13.1 DATA ANALYSES

[name], the CSA Statistician, and his staff will perform data analyses. Prior to analyses, standard data screening/cleaning procedures will be applied. These procedures will screen the data for data-entry errors, check for outliers, assess the extent and pattern of missing data, and check that appropriate assumptions of normality are met whenever necessary.

13.2 **SAMPLE SIZE DETERMINATION**

Power Analyses: The primary goal of this study is to determine if the PBG/LFX combination versus LFX/PGB-PLA is safe and effective in OUD individuals, and shows a reduction in opioid–related withdrawal effects greater than lofexidine alone. To assist in this determination, we provide power for the primary comparison of longitudinal subjective withdrawal measures, comparing the groups on rate of decrease across days, using a linear group by time effect for the mixed effects models described above. We have one primary outcome, so use an alpha level of 0.05, and we use two- sided tests. 90 subjects, approximately 30 from each of three sites (MMTC and PENN might have more than 30), who will be randomized into two groups, with 30 assigned to LFX/PGB-PLA, and 60 to LFX plus a starting daily dose of 400 mg of PGB and increasing to 600mg PGB on day 2. Assuming an overall dropout rate of 40%, and within-subjects' correlations of 0.5, the methods of Hedeker et al (Hedeker, Gibbons and Waternaux, 1999) show that this provides 80% power for a group by linear time interaction effect of Cohen's d=0.44 standard deviations between the two groups.

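### Sex is a randomisation stratum but is missing from the primary and ordinal models; the planned tests stay valid, and adding it is a nearly free improvement

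*Combined protocol and SAP*

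**What the plan says.** **Randomisation.** Section 11.1 uses permuted blocks within each site "that are stratified according to male/female".

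**Models.** Section 13.3.1 specifies: "SOWS-Gossop total will be regressed on a three-level factor for site, and a two-level factor for medication group, with time and group by time". The ordinal model in 13.3.2 has site and medication group only, as do the creatine kinase and edema models in 13.4. The 3.0 summary describes the primary model with site and group and lists no time terms. Sex appears in none of them.

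**Powered quantity.** Section 13.2 bases power on "comparing the groups on rate of decrease across days, using a linear group by time effect", and gives 80% at d = 0.44.

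**Scores.** Section 13.3.1 states: "The groups will be compared on the 14 repeated SOWS-Gossop responses obtained during the seven-day detoxification period". Table 1 schedules SOWS twice on each of Days 1 to 7, and 9.1.2 times the first: "SOWS-G is given around 12:00 on Day 1 before the first dose of study medication". Section 9.1.2 also allows repeats for subjects not yet in sufficient withdrawal: "subsequent COWS and SOWS can be administered before the first dose of study medication until dosing criteria is met". Section 7.3.3 adds: "On day 1, if dosing cannot be given at the 12:00 scheduled time, after 2 hours, wait until the next scheduled 16:00 dose".

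**The concern.** When randomisation is balanced on a factor that predicts outcome, a between-subject comparison that ignores the factor overstates its own standard error. The test stays valid but becomes conservative and loses some power. With 30 controls and 40% expected dropout, the plan has little to spare.

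A related point concerns the first Day 1 SOWS. It precedes any study drug, and randomisation comes before it whether it takes place before admission (9.0) or at admission (9.1.1). The arms therefore have equal means there in expectation. The planned model gives each arm its own intercept and does not use this fact. Section 13.3.1 also does not say whether SOWS repeated only to establish eligibility for dosing are outcomes.

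**Working it through.** **Inputs from the documents.** 60 and 30 subjects, two-sided alpha 0.05, d = 0.44 SD, within-subject correlation 0.5 and 40% dropout (13.2); 14 SOWS occasions (13.3.1); 30% women (10.4); 41% completion on lofexidine in the pivotal study cited in 7.1.5.

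**Assumptions.** The correlation is constant over time. Retention falls linearly from 1.0 to 0.6. The group difference grows linearly from 0 at the first score to d at the last, with time scaled 0 to 1. Scores are either equally spaced or at clock times (Day 1 at 12:00 and 16:00, then 08:00 and 16:00).

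**1. The plan's own power.** With columns for intercept, time, group and group by time, the information is the sum, over arms g and last occasion seen k, of n_g × p_k × X_k′V_k⁻¹X_k. Here p_k is the share of subjects last seen at k. The SE is the square root of the group by time entry of its inverse, and power = Φ(0.44/SE − 1.96).

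- Clock times: SE 0.1561; 0.44/0.1561 − 1.96 = 0.859; power 80.5%.
- Equal spacing: SE 0.1621; 0.44/0.1621 − 1.96 = 0.754; power 77.5%.

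The stated 80% reproduces at clock times.

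**2. Sex and the slope test.** A constant sex effect shifts a subject's level, while the slope contrast is within subject. With sex explaining 2%, 5% or 10% of between-subject variance, slope power (equal spacing) is 77.5% with or without it.

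**3. Sex and between-subject comparisons.** A linear model on one summary per subject was simulated with 30% women and 4:2 blocks within site by sex (20,000 null trials per case). For assumed sex effects of 0, 0.3, 0.5 and 0.8 SD, type I error without sex is 0.050, 0.048, 0.046 and 0.040; with sex it is about 0.050. Power without and with sex is 79.5% and 81.1% at 0.5 SD, and 77.3% and 81.1% at 0.8 SD.

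The ordinal model of 13.3.2 was simulated with 7,000 trials per case and exact 2:1 balance within site by sex. Control probabilities were 0.59/0.20/0.21, from 41% completion with half of completers assumed injected. The group odds ratio was assumed to be 3. Monte Carlo SE is about 0.5 points for power and 0.3 for type I error.

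| Sex odds ratio (assumed) | Power without / with sex | Type I error without / with sex |
|---|---|---|
| 1 | 74.6% / 75.0% | 5.0% / 5.2% |
| 2 | 72.4% / 74.0% | 4.7% / 5.3% |
| 4 | 66.6% / 71.4% | 3.8% / 4.9% |

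**4. Arms held equal at the pre-dose score.** Deleting the group main effect from the matrix in step 1 gives:

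| Case | SE free / constrained | Power free / constrained |
|---|---|---|
| Clock times | 0.1561 / 0.1466 | 80.5% / 85.1% |
| Equal spacing | 0.1621 / 0.1508 | 77.5% / 83.1% |
| Random-slope variance 0.5, equal spacing | 0.2431 / 0.2344 | 44.0% / 46.7% |
| Random-slope variance 1.0, equal spacing | 0.3005 / 0.2927 | 31.0% / 32.4% |
| Effect starts at mid-period, equal spacing | 0.1621 / 0.1508 | 72.1% / 72.3% |
| Effect starts at 75% of the period, equal spacing | 0.1621 / 0.1508 | 40.0% / 39.2% |

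In the mid-period row the expected slope is 0.413 free and 0.385 constrained, which offsets the smaller SE. Under an immediate step of 0.44 SD the expected coefficient is 0.188 free and 0.290 constrained, so the constrained coefficient absorbs part of a level difference.

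**5. Dependence on the time origin (equal spacing).** Moving the common origin leaves the free-intercept estimate and SE at 0.440 and 0.1621. A shift of 0.1 of the period moves the constrained ones from 0.440 and 0.1508 to 0.452 and 0.1554. If 0, 25, 50 or 100% of subjects start at 16:00 (clock times), the free model has 80.5, 80.3, 80.1 and 79.7% power. The constrained model, dropping the earlier pre-dose score, has 85.1, 83.7, 82.3 and 78.9%.

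**The case against.** The strongest reply is that nothing here is an error. The slope test is valid, its stated power reproduces, and the pre-dose score already enters the model as one of the 14 responses. The choice is then between valid models in a phase 2 trial meant to precede a larger one. Sex does nothing for the slope test, and its gain in the ordinal model rests on assumed odds ratios. This stands as to severity. It does not answer why a stratum already recorded on every subject should be left out when including it costs one parameter.

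A reader might infer that the equal-start model should replace the primary analysis. The documents do not support that. Section 13.2 powers the rate of decrease, whereas the constrained coefficient mixes rate with level. Its gain also shrinks or disappears under a random slope, which 13.3.1 permits, or a late effect.

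A reader might also infer that the primary analysis has no defined time zero. That is overstated. The planned contrast does not depend on a common origin; the constrained one does. Table 1, 9.1.2 and 13.3.1 together point to two scheduled scores on each of seven days. What remains open is only the status of the extra eligibility scores, which one sentence settles.

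**Conclusion.** The point holds as a low-cost improvement. Sex is balanced by design and then ignored in the primary and ordinal models. The consequence is slight conservatism and lost efficiency in between-subject comparisons when sex is prognostic: about 1.6 power points in the ordinal model at a sex odds ratio of 2 and 4.8 at 4, both odds ratios being assumed. If sex is not prognostic, the difference is within simulation error.

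Two further inferences should be resisted. Omitting sex does not inflate type I error; in the simulations it stays at or below about 5%. Nor is the 80% in 13.2 shown to be wrong: the 77.5% under equal spacing reflects a spacing that the plan does not specify.

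The equal-start model is worth having as support. At the inputs of 13.2, with constant correlation and linear growth, it adds 4.6 points at clock times and 5.6 at equal spacing. It adds 1.4 to 2.7 with a random slope and nothing with late onset. No added false-positive harm was found: with no effect, a curved common course and retention of 65% versus 50%, rejection was 6.0% for the free model and 5.8% for the constrained one.

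**What to change.** 1. **Sex.** Add sex as a two-level factor to the primary model in 13.3.1, to its description in the 3.0 summary, and to the ordinal model in 13.3.2. Leave the sparse-event models in 13.4 as they are.
2. **Primary contrast.** State in 13.3.1 that the primary contrast is the group by linear time effect, with a free group intercept, as powered in 13.2.
3. **Outcomes.** State that the 14 outcomes are the scheduled twice-daily scores of Days 1 to 7, and that additional SOWS taken only to check dosing eligibility are not outcomes.
4. **Supportive analysis.** Pre-specify the same model with the arms constrained to a common mean at the last SOWS before the first dose, with time measured from that score and earlier pre-dose scores left out. Note that its coefficient also reflects level differences.

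The cost is a few sentences and no new data. Sex uses one parameter per model, with about 0.30 × 90 = 27 women in the smaller level. The supportive analysis loses its power advantage if most subjects start at 16:00, which is a further reason not to make it primary.

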3.0 PROTOCOL SUMMARY

Title	Combining Pregabalin (LYRICA®) with Lofexidine (LUCEMYRA™): Can it Increase the Success of Transition to Naltrexone?						
Short Title	Pregabalin and Lofexidine for opioid withdrawal						
Protocol Version	7.0						
Phase	Phase 2						
Methodology	Double-blind placebo-controlled parallel group clinical trial						
Study Duration	24 months						
Study Centers (3)	 University of Pennsylvania Center for Studies of Addiction in Philadelphia Pennsylvania Columbia University in New York City, New York Mountain Manor in Baltimore, Maryland 						
Objective (Primary)	To investigate whether pregabalin-Lyrica® (PGB) combined with Lofexidine-Lucemyra® (LFX) can reduce opioid withdrawal-related subjective effects						
Objective (Secondary)	To investigate, if the PGB/LFX combination can increase the proportion of patients with an opioid use disorder (OUD) who complete detoxification and transition to antagonist treatment with extended- release injectable naltrexone VIVITROL® (XR-NTX)						
Number of Subjects	90 subjects. 60 randomized to PGB/LFX; 30 to PGB-PLA/LFX						
Inclusion Criteria	 Male and/or female subjects ≥ 18 years of age Meet DSM-5 criteria for an Opioid Use Disorder with physiologic features. Have 2 or more of the 11 DSM 5 criteria for opioid disorder including tolerance and withdrawal features in the last 12 months Interested in opioid antagonist treatment Have used opioids in 20 of the past 30 days Have a stable address in the local area; not planning to move; have documents for ID check Absence of medical or psychiatric conditions that are likely to interfere with study participation Have a 12 lead ECG demonstrating a QTc ≤450 msec and a QRS interval ≤120 msec. The site PI has the final determination for inclusion into the study for ECGs unless there is a question of QT prolongation or other factors (QTc/Fri uses the Fridericia formula (QTc = QT/RR(1/3)). If consultation is needed, the PENN cardiologists and the medical monitor should be contacted. If female, have a negative pregnancy test, and uses adequate contraception if of childbearing potential 						

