8.2 SECONDARY OBJECTIVES

1) To determine if PGB plus LFX will result in more successful opiate detoxifications Successful detoxification is defined as completing the 7-day regimen/dosing of either PBG/LFX or LFX/PGB-PLA without leaving the inpatient unit or otherwise withdrawing from

the study; having a SOWS score of less than 6; a COWS score of less than 9; and a urine drug screen that is negative for opioids, **excluding buprenorphine**, **and fentanyl**.

2) To determine whether PGB plus LFX improves rates of completion of detox and receipt of XR-NTX

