9.0 STUDY DESIGN

This study is a phase II, two-part randomized, double-blind placebo-controlled, study to assess the effectiveness of PGB combined with LFX to reduce opioid withdrawal- related subjective effects, and to examine whether a PGB/LFX combination can increase the proportion of opioid use disordered (OUD) subjects who transition to antagonist treatment (XR-NTX).

The study will use three sites, each with inpatient units that provide beds and care from nurses that will be trained in study procedures and dosing requirements. Each site will recruit around 30 randomized subjects, with the Mountain Manor Site and the PENN site possibly recruiting greater than 30 subjects, for a total sample size of 90, using DSM-5 to establish an OUD diagnosis with physiologic features. This trial has 4 distinct phases (see Figure 1 schematic): 1) Outpatient Screening; 2) Inpatient medication induction plus other assessments on Days 1-7; 3) Inpatient XR-NTX administration on Day 8 or 9; and 4) Outpatient Follow-Up (5 days). Total days in study is 15 days plus or minus the time taken to complete the initial outpatient screening assessments. Randomization will occur before inpatient admission.

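### The single ordinal model in 13.3.2 pools detoxification completion with XR-NTX receipt, so the plan has no analysis that answers the XR-NTX transition question on its own

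*Combined protocol and SAP*

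**What the plan says.** The protocol summary (3.0) gives the secondary objective as whether the combination "can increase the proportion of patients with an opioid use disorder (OUD) who complete detoxification and transition to antagonist treatment". Section 9.0 words it as the proportion who transition to XR-NTX. Section 8.2 has two secondary objectives: "To determine if PGB plus LFX will result in more successful opiate detoxifications", and "To determine whether PGB plus LFX improves rates of completion of detox and receipt of XR-NTX".

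Section 13.3.2 defines one ordered outcome. Level 1 is failure to complete; the other levels are "2) completion with failure to start antagonist treatment, (3) completion and receipt of antagonist treatment". The analysis is one sentence: "We will compare these groups using ordinal logistic regression models, with a three-level factor for site, and a two-level factor for medication group". The summary (3.0) defines the secondary outcome in the same three levels.

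The plan gives no separate comparison or estimate of level 3, no odds ratios by cut, no check of proportional odds, and no alpha, power or success rule for the secondary outcome. The alpha statement in the sample size section concerns the primary outcome: "We have one primary outcome, so use an alpha level of 0.05, and we use two- sided tests".

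**The concern.** The joint event in the summary and in objective 2 of 8.2 is level 3 of the outcome. A proportional-odds model does not estimate the level-3 difference by itself. It fits one group effect to two questions: did the patient complete, and did the patient complete and receive XR-NTX? If pregabalin only moves patients from level 1 to level 2, the group effect can still be significant. If pregabalin only moves completers from level 2 to level 3, the effect is diluted.

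The first pattern is conceivable here. The injection is optional, requires a passed naloxone challenge, and comes on day 8 or 9, after the day 5 to 7 taper. The pregabalin trial cited in 7.1.4 reported a completion difference (79% against 47%) without a significant difference in withdrawal severity. A trial of other regimens cited in 7.1.3 found no difference in XR-NTX transition across arms (41-46%).

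XR-NTX transition is in the trial's title, and section 7.1.6 says the results will lead into a larger trial that would also look at completion and transition. A retention signal read as a transition signal would misdirect that trial.

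**Working it through.** **Plan's own figure.** There is none on this point. The only power statement (80% for d = 0.44) concerns the primary outcome.

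**Inputs.**
- Group sizes 60 and 30, from the sample size section: "with 30 assigned to LFX/PGB-PLA, and 60 to LFX plus a starting daily dose of 400 mg of PGB".
- Two-sided 0.05: assumed for the secondary outcome.
- Completion anchors: 47% and 79% (clonidine and pregabalin arms, 7.1.4) and 41% (lofexidine arm, 7.1.5). The treated-arm values of 60% and 65% are assumptions.
- Level-3 rates: assumptions, because the plan gives no planning rate.

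**Model.** With Y the level and G the group, the usual form is logit P(Y ≥ j) = a_j + bG + site, for j = 2 (completion) and j = 3 (completion with XR-NTX). One b serves both cuts. Section 13.3.2 does not name proportional odds; this is the usual default.

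**Why one b can mislead.** Take completion 47% to 79% with level 3 at 33% in both arms.
- Odds ratio at the completion cut: (0.79/0.21)/(0.47/0.53) = 3.76/0.887 = 4.24.
- Odds ratio at the XR-NTX cut: 1.
- The model reports a single value for both.

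**Simulation.** 40,000 trials per row. The ordinal test is the tie-corrected rank-sum z, which is the score test of b = 0 without covariates. The direct test is the pooled two-proportion z on level 3. Uptake is level 3 divided by completion.

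| Completion, control to PGB | Level 3, control to PGB | Uptake among completers | Ordinal test favours PGB | Level-3 test rejects (either direction) |
|---|---|---|---|---|
| 47% to 47% | 33%, 33% | 70%, 70% | 2.4% (4.9% either direction) | 4.9% |
| 47% to 60% | 33%, 33% | 70%, 55% | 11% | 5.1% |
| 41% to 60% | 30%, 30% | 73%, 50% | 21% | 4.8% |
| 41% to 65% | 25%, 25% | 61%, 38% | 33% | 5.1% |
| 47% to 79% | 33%, 33% | 70%, 42% | 43% | 5.1% |
| 41% to 79% | 25%, 25% | 61%, 32% | 64-65% | 5.0% |
| 41% to 41% | 20%, 40% | 49%, 98% | 10% | 48% |
| 47% to 79% | 33%, 55% | 70%, 70% | 77% | 50% |

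Fitting the model with site and a Wald test gives the same picture: 24% for 41% to 60% with level 3 at 30%, and 8% for the 20% to 40% row.

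**Formula check of the 48%.** Pooled p = (24 + 6)/90 = 0.333.
- SE under the null = √(0.333 × 0.667 × (1/60 + 1/30)) = 0.1054.
- SE under the alternative = √(0.4 × 0.6/60 + 0.2 × 0.8/30) = 0.0966.
- Power = Φ((0.20 − 1.96 × 0.1054)/0.0966) = Φ(−0.07) = 47%.

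**Precision of a level-3 estimate.** For 33% against 55%, SE = √(0.55 × 0.45/60 + 0.33 × 0.67/30) = 0.107, so the 95% CI is about ±21 points around a difference of 22 points.

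**The case against.** - **The ordinal outcome is defensible.** Section 8.2 lists more successful detoxifications as a separate objective, and moving patients from level 1 to level 2 bears on it. This stands, with a limit: 8.2 defines success by SOWS, COWS and urine results, whereas completion in 13.3.2 needs only a day-7 dose and a day-7 SOWS assessment.
- **The rejections are not type I errors.** A reader might infer that the planned test has an inflated false-positive rate, or that the trial will declare success on XR-NTX without any gain. The documents do not support either reading. With no effect at all the test rejects in about 5%. In the equal-level-3 rows completion truly improves, so the model's null is false. No passage states a null or a success rule for the secondary outcome. The harm arises only if the common odds ratio is reported as a transition effect.
- **The larger figures need an awkward pattern.** Uptake among completers must fall, for example from 70% to 42%, although interest in antagonist treatment is an inclusion criterion. The 41% and 79% anchors also come from different trials. This stands: with completion 47% to 60% the figure is about 11%. The 20% to 40% row is equally extreme, because it needs nearly all treated completers to take XR-NTX (0.40/0.41 = 98%).
- **Replacing the ordinal test would lose power.** This stands too. If uptake stays at 70%, the ordinal test has 77% power and the level-3 test 50%. It argues for adding the level-3 comparison, not substituting it.

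**Conclusion.** The gap is real and limited. The transition question in 3.0, 9.0 and objective 2 of 8.2 has no estimate of its own, and the one planned group effect cannot show whether completion or XR-NTX receipt changed. With equal level-3 rates the ordinal test favours pregabalin in about 11% to 65% of trials, depending mainly on the completion gain (13 to 38 points). It has about 10% power when level 3 doubles from 20% to 40% with completion fixed at 41%. These sizes rest on assumed level-3 rates, an assumed two-sided 0.05 and the proportional-odds form. They do not make the ordinal model invalid; they show that its result alone cannot support a statement about XR-NTX.

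Level 3 is also not the same as all XR-NTX receipt. Sections 7.5.2 and 9.1.3 allow the injection for patients about to leave against medical advice. Those who leave before meeting the day-7 completion definition would be injected yet counted in level 1.

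**What to change.** In 13.3.2:
1. Keep the ordinal model as planned.
2. Add a prespecified comparison of level 3 against levels 1 and 2 in all randomised patients: logistic regression on site and group, reported as a risk difference with 95% CI.
3. Report separate odds ratios at the completion cut and the XR-NTX cut beside the common odds ratio.
4. State that any conclusion about XR-NTX transition will be drawn from the level-3 estimate and its interval, not from the common odds ratio alone.
5. Report all XR-NTX receipt by arm, whether or not detoxification was completed.

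**Cost.** One extra model, some SAP wording and no new data. Logistic models with site and group are already planned in 13.4.3 and 13.4.4. The downside is modest power, about 50% for 33% against 55%, so the level-3 result should be presented as an estimate for planning the next trial.
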